The objective of this proposal is to adapt PPE training guidelines issued by the World Health Organization (WHO)³⁶ and the U.S. Occupational Safety and Health Administration (OSHA)³³ for use by healers and to fill the current evidence-to-practice gap by comparing effectiveness of two practical strategies for implementing evidence-based PPE guidelines.

Our proposal compares two implementation strategies to increase PPE use and proper disposal during procedures and decrease the number of risky injections performed (de-implementation of traditional injections): (1) Health care worker (HCW)-led education on blood exposure risk and PPE use through a week-long training, followed by three educational outreach visits at the healer's place of practice vs. (2) "Early adopter" healer³⁷⁻⁴⁰ and HCW co-led training followed by three educational outreach visits. We hypothesize that "early adopter" healer messaging and delivery will have greater impact given their membership within the healer community.

Aim 1. Gather information about how healers and health care workers are learning about PPE use to develop an acceptable and appropriate PPE training program.

Aim 2: Compare fidelity to delivery of PPE training between the HCW-only and the healer plus HCW teams.

We will compare training fidelity of the two teams via three constructs: (1) content, (2) coverage, and (3) duration^{41,42} to determine if there is a difference in fidelity between the two types of teams.

Hypothesis 1: Training fidelity will be greater among healer + HCW teams, as they will have greater motivation to comprehensively deliver education and skill building sessions to healers.

Aim 3: Compare the effects of the two implementation strategies on healer exposure to patient blood.

We will enroll traditional healers into each PPE strategy using a stratified random sampling. Healers will use containers to collect all used sharps and used gloves over a six-month period and complete a low literacy data collection form to document glove use to identify gaps in PPE use.

Hypothesis 1: Healers who are trained by the healer + HCW team will have a higher proportion of glove use during injections than those in the HCW-only trainer arm.

4. Study Population

Population

Traditional healers and biomedical practitioners (including clinicians and nurses) providing patient care in the Bushbuckridge area.

Inclusion Criteria

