Aim 3: From preliminary data collected from healers in Agincourt in 2019, the median proportion of glove use during vaccinations was 0.44, mean 0.39, and standard deviation (SD) 0.39. Our sample size is calculated based on a two-sample t-test and incorporates these preliminary data. Assuming the SD=0.39, then we anticipate needing 61 healers per arm (total of 122) to have 80% power to detect at the ($\alpha=0.05$ -level) a difference of 0.2 in the proportion glove use between the HCW-only and the healer + HCW teams (e.g., 0.4 vs. 0.2). Included below is the variability in power given different deltas (differences in the mean proportion of blood exposure between the two arms) (Table 1). Note, that these power calculations are approximate as primary analyses will be performed using negative binomial regression. Power calculations using negative binomial regression would require assuming a distribution of the offset (number of procedures performed per healer), which substantially complicate the calculations. Therefore, we present power calculations based on two-sample t-tests, which should be fairly similar.

Table 1 Sample Size and Power

N	Δ	SD	α	P
61	0.17	0.39	0.05	66.57
61	0.18	0.39	0.05	71.52
61	0.19	0.39	0.05	76.08
61	0.20	0.39	0.05	80.22
61	0.21	0.39	0.05	83.89

61	0.22	0.39	0.05	87.08
61	0.23	0.39	0.05	89.81
61	0.24	0.39	0.05	92.09
61	0.25	0.39	0.05	93.96

N: number of healers per arm

Δ: Difference to detect (delta)

SD: Standard deviation

α: Significance level (alpha)

P: Power, %

Randomization strategy

To avoid concerns that, despite randomization, one intervention arm of healers will substantially differ from the other, we will conduct stratified randomization. Specifically, we will stratify based on healer sex and the number of patients seen in a given month (dichotomized into high/low based on the estimated median number of patients seen in the past month). This will result in 4 strata. At the time of randomization, each healer will be put in a strata and equal numbers of healers in each strata will be randomized to the two intervention arms.

5. Methods

Measurement of Results

Aim 1: We will use qualitative measures to understand the best strategies to delivery PPE training to traditional healers in Bushbuckridge.

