Aim 2: We will rate training fidelity via two constructs: (1) content and (2) coverage^{41,42} during the week-long training session and community-based outreach sessions (Appendix 2). Understanding the fidelity of training delivery is essential to interpreting the effect of the intervention on PPE behavior change. If HCW + healer teams can deliver training with greater or equal fidelity than HCWs alone, PPE training can be more quickly scaled up nationwide (given the large number of healers) and conducted at lower cost (healers charge considerably less per hour than HCWs). We believe that the healer + HCW teams may have more motivation to deliver the program with fidelity during community-based sessions than the team of HCWs alone because of healers' desire to protect their peers living in their own community. Three HCWs who volunteer to work on this project will be randomly assigned to the intervention team (along with the healers), with six volunteer HCWs assigned to the control arm.

Aim 3: Healers will complete an interviewer-assisted survey immediately post training (Appendix 3) using the Consolidated Framework for Implementation Research framework⁴³ (compatibility of PPE with current behavior, peer pressure to use PPE, perception of the inclusiveness of the training process, cost) and individual characteristics from the situated-IMB model (Figure 3)^{44,45}. During the six months of the trial, healers in each arm will record data on our primary outcome: the proportion of injections conducted using PPE in two ways.

(1) Collect used sharps and PPE. Healers will be given containers to place all used gloves and razors/sharps to both ensure healer safety and allow us to count materials used (healers use gloves and a single razor once per patient and subsequently throw them into latrines or trash piles). We will use the *number of glove pairs as the numerator* (number of times they used gloves during procedures) and the *number of razor blades as the denominator* (number of injections given). While some may be concerned with social desirability bias, healers have been told for years to use gloves and were very open with us about their non-use. Healers have no reason to

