under- or over-inflate their PPE use as it will not benefit them- in fact, they would have to buy the razor blades or travel to a health facility to obtain additional latex gloves, something that seems unlikely in this population. (2) Self-report. Healers will record behavior (injection and glove use) every time they conduct an injection.

Study Procedures

Aim 1:

Phase 1: Information Gathering: We will interview select traditional healers and health care workers who have received some training on the use and disposal of PPE. Among traditional healers we will probe into how we can improve the training they receive, their preferred method of receiving information, and perceived gaps in their knowledge. From health care workers, we will gather information about how they were trained in the donning and doffing of PPE, aspects of the training that they believe would be most useful to traditional healers, and strategies to deliver these messages in a way that would be accessible to those with low levels of literacy.

Phase 2: Production of Draft Program: After we gather information from healers and health care workers, we will produce a draft of our training program. Our team will ensure we are maintaining fidelity to core elements and the underlying theoretical framework of the original evidence-based intervention. If there are substantive changes, we will draft additional measures to assess impact of these changes on the intervention outcomes. We will also develop quality assurance metrics (e.g. to ensure healers are using and disposing of PPE safely) and process measures to track the program's success.

Phase 3: Topical Experts: With our advisory counselor, as well as local leaders (e.g. leader of the traditional healer association, head of HIV care and treatment in the Department of Health), we will elicit feedback on our draft protocol. These experts will be tasked to focus on "big picture" issues, specifically sustainability and integration into district, provincial, and national level systems.

Data Collection:

In-depth Interview Question Guide: All participants will provide feedback on the acceptability, feasibility, and appropriateness of PPE training via open-ended questions (e.g. What information was most useful?), as well as questions about perceived barriers and facilitators to PPE training (How difficult will it be to use the sharps containers?) (Appendix 1).

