Analysis plan for coverage: We will calculate the percentage of sessions completed as the actual number of sessions completed for a participant divided by the total number of planned sessions. The percentage of sessions completed between the two intervention arms will be compared using mixed effects Poisson regression with the number of planned sessions (in most cases 3) as an offset. 95% confidence intervals will be constructed. The models will include random effects for the trainers. Covariates will include patient volume, sex, and baseline age. Missing data and LTFU will be handled as described above.

Aim 3: The analysis will follow intent-to-treat protocol. Our primary outcome is the proportion of a healer's procedures that were conducted using latex gloves (numerator = number of procedures with blood exposure, denominator = number of procedures). We will compare the blood exposure proportions between the two study arms using a negative binomial regression model. In the negative binomial regression, the outcome will be the number of times gloves were used and the number of procedures performed by the healer (number of razor blades) will be included as an offset. Such an analysis is appropriate because it properly accounts for heterogeneity between healers in the number of procedures performed, and the resulting estimates from the model can be interpreted as relative proportions (proportion of procedures with blood exposure in Arm 1 vs. proportion of procedures with blood exposure in Arm 2). In addition to our primary intervention

exposure variable, we will include healer sex and baseline age as covariates in our model. Sensitivity analyses will compare blood exposure proportions between the two intervention arms using a two-sample t-test; a Wilcoxon rank sum test will be fit as needed to avoid normality assumptions.

Based on prior experience working with healers, we anticipate very low rates of loss to follow-up (LTFU). Healers who are LTFU will be censored at the time of their last recorded data collection, and inverse-probability of censoring weights based on healer characteristics randomization will be used, if necessary, to account for differences between healers who are LTFU and those who remain in the study. Missing data will be imputed using chained equations and 20 imputation replications.

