The secondary outcome, proportion of injection events, will be analyzed in a manner identical to that of our primary outcome except the outcome will be the total number of skin-cutting events performed by the healer, regardless of the use of PPE. A negative binomial regression model will be fit using the number of overall procedures as an offset. While we will not specifically look at HIV seroconversion as a study outcome, we will assess healers' baseline and end line HIV status for ethical reasons. Historical data show that the one-year incidence rate of HIV seroconversion is 1.7%. Since the incidence rate is low, we will likely not have adequate power to see a difference between intervention arms, but this information will allow us to appropriately power our subsequent R01 trial.

A separate analysis will assess each strategies' effect on PPE self-efficacy, PPE knowledge/skills, and accurate risk assessment post-training. We will explore whether the intervention effects on these measures differ by a) trainer fidelity to the intervention and/or trainer identity (healer vs. clinician), respectively. These analyses will provide quantitative data to revise and refine, as needed, the intervention for evaluation in a large RCT effectiveness study as a means of improving prevention engagement while reducing stigma.

8. Ethical Considerations

Recruitment and Consent

Aim 1: *Traditional healers* from the target community will be recruited via two strategies: (1) Healers in target catchment area are currently being mapped by two students (one from Vanderbilt and one from University of Witwatersrand). The healers are providing their address/location and contact information (phone numbers, contact for other family members) for use in future activities (including research endeavors). The healers will be contacted and given general information about the proposed study. All healers will be invited to community meetings where more information about the study procedures and aims will be provided. (2) The Kukula Traditional Healers association- the primary healer organization in the region- will hold 3 meetings to recruit healers interested in participating. Healers who express interest will be given the option for dates/locations where we will conduct recruitment fairs or the option to have a study assistant visit them at home. All recruitment will be conducted in a private room or at the home of the healer (as per the participants preference).

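### The secondary outcome model cannot show fewer injections: on the plan's own definitions its offset is the same count as its outcome

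*Combined protocol and SAP*

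**What the plan says.** Section 2 (Objectives) gives both strategies two purposes: more PPE use with proper disposal, and fewer risky injections.

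The second purpose is analysed only in Section 7 (Data Analysis, Aim 3). The secondary outcome is labelled a proportion of injection events. It is to be "analyzed in a manner identical to that of our primary outcome except the outcome will be the total number of skin-cutting events", counted with or without PPE, and "A negative binomial regression model will be fit using the number of overall procedures as an offset".

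The terms are defined in two other places:

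- Section 7, primary analysis: "the number of procedures performed by the healer (number of razor blades) will be included as an offset".
- Section 5 (Measurement of Results, Aim 3): the "number of razor blades as the denominator", which the same sentence explains as the number of injections given. That section also says one razor is used per patient.

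Overall procedures has no separate definition.

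The other activity data described are:

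- Self-report, Section 5: "Healers will record behavior (injection and glove use) every time they conduct an injection". Section 2 says healers will "complete a low literacy data collection form to document glove use to identify gaps in PPE use".
- Patient volume at randomization, Section 4: "dichotomized into high/low based on the estimated median number of patients seen in the past month".

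**The concern.** An offset fixes the quantity against which the outcome is expressed as a rate. If it is the same count as the outcome, the rate is one for every healer and no arm effect can appear. The trial would then have no working test of one of its stated purposes, and a ratio of 1.00 could be misread as evidence that the strategies do not differ.

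If a wider denominator was intended, the plan does not say what it is or where it comes from. Someone would have to choose it after the data are in. The result would also depend on how non-cutting treatments change, so a real fall in injections could be diluted or missed.

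Healers who stop injecting raise a further problem. With a razor-blade offset their term is log(0), which is undefined, so those who most fully achieve the aim could drop out of an intent-to-treat analysis.

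**Working it through.** **The plan's own figure.** The documents give no power for the secondary outcome. For the primary outcome (difference 0.20, SD 0.39, 61 per arm), an exact two-sided two-sample t-test at 0.05 gives 80.22%, matching Table 1. The other eight rows also match to two decimals. Nothing below affects that calculation.

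**Razor-blade reading, one data source.** Let N_i be the razor blades returned by healer i. Procedures are razor blades (Section 7) and razor blades are injections (Section 5), so outcome and offset are both N_i:

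log E(N_i) = log(N_i) + b0 + b1 × arm + covariate terms.

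Setting every coefficient to 0 gives a fitted value of N_i for every healer, a perfect fit. The arm ratio is exp(0) = 1.00. This is algebra and needs no assumption about the data.

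**Razor-blade reading, two data sources.** Suppose self-reported injections are the outcome and razors the offset, with an assumed 90% of injections reported in both arms. The expected ratio is (0.9N/N)/(0.9N/N) = 1.00. The model then measures agreement between two counts of the same thing.

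**Wider reading.** Assume the comparison arm has 1 injection and K non-cutting treatments per unit of time, and injections halve in the other arm (true ratio 0.50). None of these values comes from the documents.

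| Non-cutting treatments in the arm with fewer injections | Ratio of shares | Result |
|---|---|---|
| Unchanged, K = 0.5 | [0.5/(0.5+0.5)] / [1/1.5] | 0.75 |
| Unchanged, K = 1 | [0.5/(0.5+1)] / [1/2] | 0.67 |
| Unchanged, K = 3 | [0.5/(0.5+3)] / [1/4] | 0.57 |
| Replace every lost injection | [0.5/(1+K)] / [1/(1+K)] | 0.50 |
| Fall in the same proportion | [0.5/(0.5+0.5K)] / [1/(1+K)] | 1.00 |

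**Simulation.** Two sets were run, both with 61 healers per arm and an assumed 30 injections per healer over six months in the comparison arm (5 per month).

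1. Dispersion 1, true ratio 0.50, 300 trials. Razor-blade offset: 1.00 in every trial. Self-report over razors at 90% reporting: mean 1.00 (range 0.96 to 1.05). Log(months) offset: mean 0.50.
2. Gamma between-healer variation with shape 1.5, 400 trials at each true ratio. Zero counts were set to one. The shared-offset and share models were fitted as Poisson, the months model as negative binomial over a common six months.

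| True ratio (set 2) | Shared offset: ratio, rejection | Share, other treatments unchanged (K = 1) | Months: ratio, rejection |
|---|---|---|---|
| 1.00 | 1.00, 0% | 1.00 | 1.00, 6% |
| 0.75 | 1.00, 0% | 0.86 | 0.75, 50.5% |
| 0.50 | 1.00, 0% | 0.67 | 0.50, 99.5% |
| 0.25 | 1.00, 0% | 0.40 | 0.25, 100% |

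A single negative binomial fit with the shared offset, on arm means of 29.4 and 14.9 injections, gave a log ratio of about 2 × 10⁻¹³. The rejection rates in the months column depend on the assumed mean and dispersion, because the documents give no injection-count data.

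**The case against.** The strongest reply is that the authors meant something wider. A proportion of injections among injections is meaningless, and the word overall is new in that sentence, so all treatments may have been intended. An identical outcome and offset would also be noticed at the first fit, so a false null is unlikely to be published. On the wider reading the share moves in the right direction unless all treatments fall together, and a share has the merit of adjusting for workload.

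Part of this stands. The wider reading may be the intended one, and a share is a legitimate estimand. But the text says the analysis differs from the primary only in its outcome, and it gives procedures no other definition. No follow-up count of non-cutting treatments is described. The healer form is not reproduced, so one cannot say such a count will not be collected, only that the plan does not provide for it. Section 2 also speaks of the number of injections, which a share does not measure. Noticing the problem at the first fit would still leave the denominator to be chosen post hoc.

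A second reply is that razors per month assumes equal capture of used razors in both arms, although training targets disposal. That is fair. As an illustration with assumed values and a true ratio of 0.50, capture of 90% in the arm with fewer injections and 70% in the other gives 0.50 × 0.9/0.7 = 0.64; the reverse gives 0.50 × 0.7/0.9 = 0.39. The limitation applies equally to the primary denominator, which is also razor blades. It is a reason for a self-report sensitivity analysis, not for keeping the present offset.

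**Conclusion.** The concern holds. As written, the secondary model returns an arm ratio of 1.00 whatever the intervention does; that rests only on the plan's definitions. With self-report over razors it averages 1.00, provided reporting is equal in the two arms. On the wider reading the denominator has no described source, and for an assumed halving of injections the ratio lies between 0.50 and 1.00 in the scenarios examined.

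This should be fixed before analysis. It is a secondary outcome without its own power calculation, and neither the primary outcome nor its sample size is affected. The data already planned can answer the question; the specified model cannot.

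**What to change.** Define the secondary outcome as injections, counted as razor blades, per healer-month. Fit the negative binomial model with log(months of container collection) as the offset. Count months up to the last recorded collection, in line with the existing rule that "Healers who are LTFU will be censored at the time of their last recorded data collection". Healers with zero injections then stay in the intent-to-treat analysis.

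Name razor counts as the data source and self-reported injections as a sensitivity analysis. State that the razor analysis assumes equal capture in both arms, and say how a month with no razors is told apart from a container that was not returned. Reconcile the collection interval: Section 5 (Study Procedures) has monthly visits, while the healer interview guide in Appendix 1 mentions weekly collection.

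The core change is SAP wording only, because razor counts and collection visits are already planned.

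If the sponsor wants the share of treatments that are injections, the plan should say so, define the denominator and its source, and count all treatments prospectively in both arms. That adds data collection and must be settled before follow-up starts.

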3. How do you train them in the donning, doffing and disposal of personal protective equipment? What type of PPE do you train on (e.g. gloves, masks, surgical gowns, hair nets, foot coverings, visors)? (Probes: How do you tailor this to the type of student you are teaching? what kinds of difficulty do trainee's experience? How to you help them overcome those challenges?)
4. How has the training changed since COVID-19? Have you noticed a change in the use of PPE during COVID (probes: do you think health care workers are using PPE more appropriately during COVID)?
5. Once students have their basic training how frequently do you think they need refresher training? What are common mistakes health care workers make once they get accustomed to using PPE. How do they let their guards down?

6. What role does peer pressure from other providers (or more senior staff [e.g. consultant or head matron]) have in the proper use or misuse of PPE? How do you create a positive culture? How do you overcome one that is problematic?
7. We are planning to train traditional healers to properly use PPE in an effort to protect them from infectious disease. If you were to train a lay person, thinking specifically about traditional healers, how would you approach it? What topics would you focus on? What challenges do you imagine encountering?
8. What types of reinforcement or retraining would you imagine they would need?

Front Line Health Care Providers

Demographics:

Age (years)

Gender (M/F/Trans/Non-binary)

Race (Black, White, Indian, Coloured)

Name of hospital/university/clinic where you work?

Position

Number of years practicing as a health care worker?

Main Questions

1. Tell me about the PPE training you have received during your training? (Probe: what did they teach you?) Who provided the training? (Probe: where did you receive it [hospital, offsite, part of orientation?]; who gave the training [scrub nurse, ID physician, microbiologist?]). What strategies did they suggest employing to use it correctly? Did you have any difficulties using and disposing of PPE?
2. Think back to your first clinical rotation after graduation. How well were other health care providers using PPE? What were people doing correctly? How were they using PPE incorrectly?
3. Did your PPE use change after you began working? What role does peer pressure from other providers (or your seniors) have on your use of PPE?
4. Can you describe any issues accessing or disposing of PPE at your health facility? Probe: is this infrequent? What steps are being taken to fix the issue?)
5. Did you have any refresher training on the use or disposal of PPE before COVID hit South Africa? (What did the training include? If you had a previous training, did it change your use of PPE?)

5. During COVID-19, has your health facility provided additional PPE training and resources? What did the training include? How effective was it at changing PPE behavior in your facility? Changing your behavior?

6. Have you ever tried to train a lay person to use PPE? Can you tell me about that experience? What were the challenges?

7. We are planning to train traditional healers to properly use PPE in an effort to protect them from infectious disease. If you were to train a lay person, thinking specifically about traditional healers, how would you approach it? What topics would you focus on? What challenges do you imagine encountering?

8. What types of reinforcement or retraining would you imagine they would need?

9. Is there anything else about PPE use that you think we should know about before we start this study?

10. With regards to PPE, what have you found to be the most effective way at conveying both the theory and practical aspects of PPE during training? If you have been involved in multiple PPE trainings or refresher trainings, which one did you feel was the most effective and why? (Probe: Did the person giving the training affect the effectiveness of the training? If so, what type of person gave the training [e.g. ID physician, scrub nurse, etc.] Was the training organized better? If so, describe.)

Traditional Healers

Demographics:

1. Sex of respondent. 0= Male 1= Female

These are some general questions about you and your life.

2. How old are you today (age in years)?

3 What is the highest grade of education that you have completed?

4. What languages do you speak fluently? (check those English that apply)

Shangaan

Afrikaans

Portuguese

Zulu

Xhosa

Other

5. What community do you live in?

6. What is your marital status?

1= Single

2= Married

3= Living with partner

4= Widowed

5= Divorced

6= Separated

7. What religion are you? (list options)

8. Are you in a polygamous relationship (do you/ does your partner have multiple wives)? Yes No

9. How many years have you been practicing as a traditional healer? _____

10. What type of traditional healer do you MOST identify as?

1= traditional healer

2= Religious healer (Muslim)

3= Religious healer (Christian)

4= Herbalist

5= Prophet

8= Other

8a. If other, please specify:

11. Have you ever received an HIV test? Yes No

12. If you are willing to share the results, what were they?

0= Refused to share

1= Negative

2= Positive

3= Don't know/ didn't return for results

4= Indeterminate

13. HIV Rapid Test Results (baseline and end line, only used if negative or no results from prior test, we don't re-test positives)

1= Negative

2= Positive

4= Indeterminate

5= Refused Test

Demographics for health care providers

1. Sex of respondent. 0= Male 1= Female

2. How old are you today (age in years)?

3 What is the highest grade of education that you have completed?

4. What languages do you speak fluently? (check those English that apply)

Shangaan

Afrikaans

Portuguese

Zulu

Xhosa

Other

5. What community do you live in?

6. What is your marital status?

1= Single

2= Married

3= Living with partner

4= Widowed

5= Divorced

6= Separated

7. What is your current clinical position?

8. Health care facility where you are employed?

Main Questions:

1. Can you tell me about any training you have received to use gloves and/or a mask or face shield when you are treating a patient? Who provided this training? What are the skills you have learned?

2. Can you tell me if you use gloves during each procedure where you could be exposed to blood? If you don't use gloves, do you use something else, like a plastic bag?
3. If you do not always use gloves, can you tell us why? Probe: cost, access, don't believe in germ theory of disease, God will save me) Are there specific patients where you ensure that you always wear gloves? (e.g., someone you suspect has HIV?)
4. Now that COVID is widespread, do you use a mask when you have patients in your hospital or home? If you don't use a mask, can you tell me why not? Are there specific patients where you always use a mask? (e.g., someone you suspect has COVID-19 or TB?). If you use a mask, what type of mask do you use (e.g. cloth, surgical [the blue looking ones], N95)? Where did you get the mask? If you had to pay for the mask, how much did you pay?
5. How has COVID affected your physical interaction with patients? Do you see patients in person (more or less than before)? Do you talk to patients over the phone (more or less than before)? If you see patients in person have you changed the way that you do anything (length of consultant, change in traditional vaccinations or other procedures?)
6. What effect has COVID had on you as a traditional healer?
5. Have you ever had a patient ask you about your gloves/mask use? If so, did this happen during the current COVID situation? What did the patient ask and what was your response?
5. We want to provide training to you and your colleagues to ensure traditional healers are protected from infectious diseases. Would you prefer to learn these lessons from another traditional healer or from a health care provider? Why? What do you think are the most important lessons for you to learn?
6. Lets talk about disposal of gloves for a moment. When you decide that you need to protect your hands, do you put gloves/bags on both hands or only one? Do you reuse them or dispose of them? If you reuse them, how do you clean them? If you dispose of them, where do you put them?
7. Lets talk about disposal of masks for a moment. What kind of masks are you using, one that can be washed or one that needs to be disposed of? If you use one that can be washed, how often do you wash it? If you use a disposable one, where are you getting them? How long do you use it before putting it in the trash?
8. We will be providing sharps containers and containers for used gloves/bags and razor blades for those healers who enroll in the study. We will come by every week to collect these materials. Do you think anyone would have difficulty using it?
9. Our aim in providing this training and material is to ensure traditional healers are protected from infectious disease. Besides the training, masks, gloves and sharps containers. As a traditional healer, is there anything else that you think we should be discussing or considering? If so, what?
9. Is there anything else about glove or mask use that you think we should know about?

